### **3.6. Visit Windows**

#### **3.6.1. Definition of Study Day**

Study day is the day relative to the date of the first dose of study drug. Study Day 1 will be defined as the day of first dose of study drug administration.

Study day will be calculated from the date of first dose of study drug administration and derived as follows:

- For postdose study days: Assessment Date – First Dose Date + 1
- For days prior to the first dose: Assessment Date – First Dose Date

The last dose date will be the end date on study drug administration eCRF for the record where the “subject permanently discontinued” flag is ‘Y’. The last dose date will be defined as the

maximum of the last dose dates of the study drugs. If there are subjects for whom the date of last study drug is unknown due to the reason that the subject was lost to follow-up and not able to be contacted, the date of last dose will be estimated using the maximum of nonmissing study drug start or stop dates, visit dates, and laboratory collection dates (posttreatment visits and unscheduled visits are not included).

### 3.6.2. Analysis Windows

Subject visits might not occur on protocol-specified days. Therefore, for the purposes of analysis, observations will be assigned to analysis windows.

In general, the baseline value will be the last nonmissing value on or prior to the first dose date of study drug.

HCV RNA, vital signs, and safety laboratory data collected up to the last dose date + 3 days are considered to be on-treatment data and HCV RNA, vital signs, and safety laboratory data collected after the last dose date + 3 days are considered posttreatment data. The analysis windows for on-treatment HCV RNA, vital signs and safety laboratory data are provided in Table 3-1.

**Table 3-1. Analysis Windows for On-treatment HCV RNA, Vital Signs and Safety Laboratory Data**

Nominal Visit	Nominal Day	Lower Limit	Upper Limit
Baseline	1	(none)	1
Week 1	7	2	11
Week 2	14	12	21
Week 4	28	22	42
Week 8	56	43	70
Week 12	84	71	98

HCV RNA, vital sign, and safety laboratory data collected after the last dose date + 3 days will be assigned to the posttreatment follow-up (FU) visits. Visit windows will be calculated from the last dose date (ie, FU Day = collection date minus the last dose date) as shown in Table 3-2.

**Table 3-2. Analysis Windows for Posttreatment HCV RNA, Vital Signs and Safety Laboratory Data**

Nominal FU a Visit	HCV RNA			Vital Signs and Safety Laboratory Data b		
	Nominal FU Day	Lower Limit	Upper Limit	Nominal FU Day	Lower Limit	Upper Limit
FU-4	28	21	69	28	4	30
FU-12	84	70	146	NA	NA	NA
FU-24	168	147	210	NA	NA	NA

a. FU-x visit = posttreatment Week-x follow-up visit.

b. Vital signs and safety labs will only be summarized for the FU-4 visit (up to 30 days after last dose).

ECG data collected up to the last dose date + 3 days are considered to be on-treatment data. Qualitative assessments of whether the ECG is normal or abnormal will be assessed for on-treatment data based on the visit windows as shown in Table 3-3.

**Table 3-3. Analysis Windows for On-treatment ECG Data**

Nominal Visit	Nominal Day	Lower Limit	Upper Limit
Baseline	1	(none)	1
Week 1	7	2	45
Week 12	84	46	(none)

Note: ECGs are to be collected at screening, Day 1, Week 1, and Week 12 or End of Treatment. For purposes of analysis, baseline value will be the last available value prior to the first dose of study drug and end of treatment value will be the last available value on or prior to the last dose date + 3 days.

**3.6.3. Selection of Data in the Event of Multiple Records in an Analysis Window**

Depending on the statistical analysis method, single values may be required for each analysis window. For example, change from baseline by visit usually requires a single value, whereas a time-to-event analysis would not require 1 value per analysis window.

If multiple valid nonmissing numeric observations exist in an analysis window, records will be chosen based on the following rules if a single value is needed:

- For baseline, the last available record on or prior to the date of the first dose of study drug will be selected. If there are multiple records with the same time or no time recorded on the same day, average (arithmetic mean) will be used for the baseline value.
- For postbaseline visits:
  - The record closest to the nominal day for that visit will be selected except for HCV RNA posttreatment follow-up visits, for which the latest record in the analysis window will be selected.
  - If there are 2 records that are equidistant from the nominal day, the later record will be selected.
  - If there is more than 1 record on the selected day, the average will be taken, unless otherwise specified.
- If multiple valid nonmissing categorical observations exist in a window, records will be selected as follows:
  - For baseline, the last available record on or prior to the date of the first dose of study drug will be selected. If there are multiple records with the same time or no time recorded on the same day, the value with the lowest severity will be selected (eg, normal will be selected over abnormal). If multiple ECG measurements occur on the same day prior to the first dose of any study drug, the value with the lowest severity will be selected regardless of the timing of these multiple ECG measurements.
  - For postbaseline visits, follow the same rules described above for postbaseline numeric observations, except that if there are multiple records on the same day, the most conservative value will be selected (eg, abnormal will be selected over normal).

## 4. SUBJECT DISPOSITION

### 4.1. Subject Enrollment and Disposition

A summary of subject enrollment will be provided for each country and investigator. The summary will present the number and percentage of subjects in the Safety Analysis Set. For each column, the denominator for the percentage calculation will be the total number of subjects analyzed for that column.

A summary of subject disposition will be provided by genotype and overall. This summary will present the number of subjects screened, the number of subjects not enrolled, the number of subjects enrolled, the number of subjects enrolled but never treated, the number of subjects enrolled and treated (ie, safety analysis set), in FAS, and the number and percentage of subjects in each of the categories listed below. The denominator for the percentage calculation will be the total number of subjects in the Safety Analysis Set for each column.

- Continuing study treatment (if applicable)
- Completed study treatment
- Did not complete study treatment with reasons for premature discontinuation of study treatment
- Completed study
- Did not complete the study with reasons for premature discontinuation of study

Among subjects who completed study treatment and who discontinued study treatment, the number and percentage of subjects will be summarized for:

- Who had no HCV posttreatment Week 4 assessment and thereafter (No HCV FU-4 Assessment and thereafter)
- Who had HCV posttreatment Week 4 assessment but no HCV posttreatment Week 12 and thereafter (With HCV FU-4 but No FU-12 and thereafter)

If a subject did not have any HCV RNA assessment  $\geq 21$  days after the last dose of any study drug (ie, lower bound of FU-4 visit for HCV RNA data), the subject is categorized as having “No HCV FU-4 and thereafter.” If a subject had the HCV FU-4 assessment but did not have any HCV RNA assessment  $\geq 70$  days after the last dose of any study drug (ie, lower bound of FU-12 visit for HCV RNA data), the subject is categorized as having “With HCV FU-4 but No FU-12 and thereafter.”

In addition, the total number of subjects who were enrolled, and the number of subjects in each of the disposition categories listed above will be depicted by a flowchart.

The following by-subject listings will be provided by subject ID number in ascending order to support the above summary tables:

- Disposition for subjects who complete study treatment and study
- Disposition for subjects who did not complete study treatment and/or study with reasons for premature discontinuation of study treatment and/or study
- Lot number and kit ID (if applicable)

#### **4.2. Extent of Exposure**

Extent of exposure to study drug will be examined by assessing the total duration of study drug exposure and the level of adherence to the study drug regimen specified in the protocol.

##### **4.2.1. Duration of Exposure to Study Drug**

Total duration of exposure to study drug will be defined as last dose date minus first dose date plus 1, regardless of any temporary interruptions in study drug administration, and will be expressed in weeks using up to 1 decimal place (eg, 4.8 weeks).

The total duration of exposure to study drug will be summarized using descriptive statistics (n, mean, SD, median, Q1, Q3, minimum, and maximum) and using the number (ie, cumulative counts) and percentage of subjects exposed through the following time periods: Baseline (Day 1), Week 1 (Day 7), Week 2 (Day 14), Week 4 (Day 28), Week 8 (Day 56), and Week 12 (Day 84). A 3-day window is applied to the last planned on-treatment visit to match with the protocol-specified visit window, ie subjects will have number of subjects exposed through Week 12 calculated as the number of subjects who were exposed study drug for at least 81 days. Summaries will be provided by genotype and overall for the Safety Analysis Set.

##### **4.2.2. Adherence to Study Drug**

The presumed total number of tablets administered to a subject will be determined by the data collected on the drug accountability CRF using the following formula:

$$\text{Total Number of Doses Administered} = \left( \sum \text{No. of Tablets Dispensed} \right) - \left( \sum \text{No. of Tablets returned} \right)$$

The level of adherence to the study drug regimen will be assessed based on the total amount of study drug administered relative to the total amount of study drug prescribed at baseline.

The level of adherence will be expressed in percentage using the following formula:

$$\text{Level of Adherence (\%)} = \left( \frac{\text{Total Amount of Study Drug Administered}}{\text{Total Amount of Study Drug Prescribed at baseline}} \right) \times 100$$

Note: If calculated adherence is greater than 100%, the result will be set to 100%.

In this study, the total amount of SOF/VEL (400/100 mg) prescribed for 12 weeks would require 84 tablets.

Subjects who prematurely discontinue study drug for lack of efficacy (ie, virologic failure) will have the total amount of study drug prescribed calculated up to the first date when virologic failure criteria were met. For virologic failure confirmed by 2 consecutive measurements, the date of the first measurement will be used. If study drug bottles are dispensed on or after the subject first met virologic failure criteria, these bottles will not be included in the calculation of adherence. If a bottle is dispensed and the bottle is returned empty, then the number of tablets returned will be entered as zero. If a bottle is dispensed but not returned (missing), the number of tablets taken from that bottle will be counted as zero.

Descriptive statistics for the level of adherence (n, mean, SD, median, Q1, Q3, minimum, and maximum) with the number and percentage of subjects belonging to adherence categories (eg,  $\{< 80\%, \geq 80 \text{ to } < 90\%, \geq 90\%\}$ ) will be provided by genotype for the Safety Analysis Set. Categorical displays also will be provided for the number of subjects who are at least 80% adherent to their drug regimen (ie, adherence is  $\geq 80\%$  for each of the study drugs).

No inferential statistics will be provided for duration of exposure and adherence to study drug.

A separate by-subject listing of study drug administration and drug accountability will be provided by subject ID number (in ascending order) and visit (in chronological order).

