### 1.2. Study Design

This is a multi-center, open-label study of adult subjects with chronic HCV that will evaluate the safety, tolerability and antiviral efficacy of SOF/VEL FDC for 12 weeks in subjects with chronic HCV infection.

Approximately 120 subjects will be enrolled to receive: SOF/VEL (400 mg/100 mg) once daily for 12 weeks.

Up to 20% of subjects enrolled in the study may have cirrhosis at baseline and up to approximately 20% may be treatment-experienced.

The total time to complete all study visits is approximately 40 weeks including:

- 28 day (4 weeks) screening period (or can be extended to 42 days)
- 12 week treatment period
- Up to 24 week posttreatment period

The schedule of assessments is provided as an appendix to the SAP (Appendix 1).

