### **6.2. Secondary Efficacy Endpoints**

#### **6.2.1. Definition of Secondary Efficacy Endpoints**

Secondary efficacy endpoints include the following:

- The percentage of subjects with HCV RNA < LLOQ at 4 and 24 weeks after discontinuation of treatment (SVR4 and SVR24)
- The percentage of subjects with HCV RNA < LLOQ while on treatment by study visit
- HCV RNA ( $\log_{10}$  IU/mL) and change from baseline in HCV RNA ( $\log_{10}$  IU/mL) through end of treatment (EOT)
- The percentage of subjects with virologic failure as the following:
  - On-treatment virologic failure
    - HCV RNA  $\geq$  LLOQ after having previously had HCV RNA < LLOQ, while on treatment, confirmed with 2 consecutive values (note, second confirmation value can be posttreatment), or last available on-treatment measurement with no subsequent follow up values (ie, breakthrough)

- $> 1 \log_{10}$  IU/mL increase in HCV RNA from nadir while on treatment, confirmed with 2 consecutive values (note, second confirmation value can be posttreatment), or last available on-treatment measurement with no subsequent follow up values (ie, rebound)
- HCV RNA persistently  $\geq$  LLOQ through 8 weeks of treatment (ie, nonresponse)

— Relapse

- HCV RNA  $\geq$  LLOQ during the posttreatment period having achieved HCV RNA  $<$  LLOQ at end of treatment, confirmed with 2 consecutive values or last available posttreatment measurement
- Characterization of HCV drug resistance substitutions at baseline, during, and after therapy with SOF/VEL

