## **11. APPENDICES**

Appendix 1      Schedule of Assessments

**Appendix 1 Schedule of Assessments**

**Appendix Table 1. Screening, On-Treatment Visits**

	Screening (Day -28 to Day 0)	Day 1	On-treatment Study Week (± 3 days)					Post treatment Study Week (± 5 days) i		
			1	2	4	8	12/ET	4	12	24
Clinical Assessments										
Informed Consent	X									
Determine Eligibility	X	X								
Medical History	X	X								
Physical Examination	X	X					X			
Height	X									
Weight	X	X					X	X		
Vital Signs b	X	X	X	X	X	X	X	X		
12-Lead ECG c	X	X	X				X			
AEs	X	X	X	X	X	X	X	X		
Concomitant Medications	X	X	X	X	X	X	X	X		
Pregnancy Prevention Counseling		X			X		X	X		
Health Related Quality of Life Survey, SF-36		X			X		X	X	X	
Review of Study Medication Compliance g			X	X	X	X	X			
Study Drug Dispensing a		X			X	X				

	Screening (Day -28 to Day 0)	Day 1	On-treatment Study Week (± 3 days)					Post treatment Study Week (± 5 days) i		
			1	2	4	8	12/ET	4	12	24
Laboratory Assessments										
Hematology, Chemistry	X	X	X	X	X	X	X	X	X	
Coagulation Tests	X	X					X			
HCV RNA	X	X	X	X	X	X	X	X	X	X
Viral Sequencing		X	X	X	X	X	X	X	X	X
Pregnancy Testing d	X	X			X	X	X	X		
Urinalysis, Urine Drug Screen	X									
HCV Genotyping,	X									
HCV, HIV, HBV Serology	X									
HbA1c, Cirrhosis assessment (Fibrotest ® and APRI)	X									
Optional Archive Sample f		X					X			
IL28B		X								
Pharmacogenomic Sample e		X								
Imaging for Hepatocellular Carcinoma (HCC)	X									

- a. Day 1 assessments must be performed prior to the first dose of the study drug(s)
- b. Vital signs include resting blood pressure, pulse, respiratory rate and temperature.
- c. Subjects will be required to rest in a supine position for ≥ 5 minutes prior to making a recording. The investigator (or qualified designee) should review the ECG traces recorded in real time for gross abnormalities.
- d. For female of child bearing potential only. Serum β-hCG at screening, urine pregnancy test on Day 1 and every 4 weeks on treatment visits.
- e. For subjects who provide their additional and specific consent, an optional blood sample will be collected at the Baseline/Day 1 visit for PG (this sample may be drawn after Baseline/Day 1 if necessary).
- f. Subjects may opt out of archive sample collection.

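### Adherence in subjects stopped for virologic failure: the denominator is cut by date and the numerator by bottle, so a failure first met between dispensing visits can overstate adherence

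*SAP*

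**What the plan says.** SAP Section 4.2.2 defines adherence as study drug administered divided by study drug prescribed at baseline. The numerator is tablets dispensed minus tablets returned, "determined by the data collected on the drug accountability CRF". For the full course, "the total amount of SOF/VEL (400/100 mg) prescribed for 12 weeks would require 84 tablets".

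Subjects who discontinue early for virologic failure have their own rule:

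- **Denominator.** They "will have the total amount of study drug prescribed calculated up to the first date when virologic failure criteria were met". Where failure is confirmed by two consecutive measurements, the date of the first one applies.
- **Numerator.** "If study drug bottles are dispensed on or after the subject first met virologic failure criteria, these bottles will not be included" in the calculation. Bottles dispensed earlier count in full, with no date cut inside a bottle.
- **Cap, for all subjects.** "If calculated adherence is greater than 100%, the result will be set to 100" per cent.
- **Unreturned bottle, for all subjects.** No tablets are counted as taken from it.

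Section 6.2.1 has breakthrough and rebound "confirmed with 2 consecutive values (note, second confirmation value can be posttreatment"), or established by a last on-treatment value with no follow-up. Nonresponse is judged through 8 weeks of treatment. In Appendix Table 1 the row "Study Drug Dispensing" is marked at Day 1, Week 4 and Week 8, whereas HCV RNA is also sampled at Weeks 1 and 2.

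**The concern.** The two terms of the ratio can cover different periods in the same subject. The bottle exclusion shows that the plan means to leave out drug taken after failure, but it achieves this only when a dispensing coincides with, or follows, the first failing sample. If that sample falls mid-bottle and the subject keeps dosing, the later tablets count as administered although none are counted as due on those days. The ratio then rises, possibly past 100%, and the cap makes it look like ordinary full adherence in the summary tables.

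The value feeds three outputs: the adherence summary by genotype, the count of subjects at least 80% adherent (both Section 4.2.2), and the SVR12 subgroup split at 80% (Sections 3.3 and 6.1.3). A treatment failure who was under 80% adherent up to failure could appear in the group at or above 80%.

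**Working it through.** **Inputs from the SAP.** One tablet "once daily for 12 weeks" (Section 1.2); the full-course denominator of 84, the failure rule and the cap (Section 4.2.2); dispensing at Day 1, Week 4 and Week 8 and a ±3-day on-treatment window (Appendix Table 1); about 120 subjects (Section 1.2).

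**Assumptions.** Bottle size is not stated; 84/3 = 28 tablets per dispensing is used. The number of tablets taken after the first failing sample is illustrative, since the SAP gives no interval between that sample and the stop. For failure at Week 2 the denominator is taken as 14, with a range of 13 to 15 because it is not fixed whether the failure day itself counts.

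**The plan's own figure.** 12 weeks × 7 days × 1 tablet = 84. It reproduces.

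**Formula.** Reported adherence = min(100%, tablets counted / tablets prescribed up to first failure). The comparator cuts both terms at the first failure date.

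**Failure first met between dispensings**

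| First failure | Taken by then | Taken later, same bottle | Both terms cut at failure | SAP rule | SAP rule, denominator 13 to 15 |
|---|---|---|---|---|---|
| Day 14 | 10 | 4 | 10/14 = 71.4% | 14/14 = 100% | 100% (capped) to 93.3% |
| Day 14 | 7 | 5 | 7/14 = 50.0% | 12/14 = 85.7% | 92.3% to 80.0% |
| Day 14 | 7 | 7 | 7/14 = 50.0% | 14/14 = 100% | 100% (capped) to 93.3% |
| Day 14 | 14 | 14 | 14/14 = 100% | 28/14 = 200%, capped to 100% | 100% (capped) throughout |
| Day 42, unscheduled | 32 | 7 | 32/42 = 76.2% | 39/42 = 92.9% | not applicable |
| Day 42, unscheduled | 32 | 14 | 32/42 = 76.2% | 46/42 = 109.5%, capped to 100% | not applicable |

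The fourth row shows that the literal rule can give twice the possible maximum. There the cap happens to restore the right value; in the other capped case it does not.

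**Failure first met at a dispensing visit**

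The bottle handed out that day is excluded, so the most that can be counted is:

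- Week 4: 28/28 = 100% on Day 28, 28/25 = 112.0% on Day 25 (capped), 28/31 = 90.3% on Day 31.
- Week 8: 56/56 = 100% on Day 56, 56/53 = 105.7% on Day 53 (capped), 56/59 = 94.9% on Day 59.

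With 21 of 28 tablets taken and the rest returned on Day 28, both methods give 75.0%. Only if the 7 left over are kept and taken later does the SAP rule give 28/28 = 100%.

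**Opposite direction.** If the only bottle is never returned, failure at Day 14 gives 0/14 = 0%.

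**Weight in the summary.** One subject in the wrong class is 1/120 = 0.8 percentage points of the whole trial, and more within a genotype. The SAP gives no expected number of such subjects.

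**The case against.** The strongest reply is that this is a corner case. Nonresponse is judged at Week 8, a dispensing visit. Breakthrough needs an earlier on-treatment value below LLOQ, and the first scheduled one is at Week 1, so scheduled breakthrough cannot be seen before Week 2. The confirming value may be posttreatment, so dosing need not continue while it is awaited. Adherence is descriptive, and the subgroup is one of twelve characteristics to be explored. All of this stands and limits the reach of the point. It does not remove the mismatch where the rule is followed as written.

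Four stronger readings are tempting, and the SAP does not support them:

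- **That every subject stopped for virologic failure is affected.** The bottle exclusion largely deals with failure first met at Week 4 or Week 8.
- **That the rule always errs upward.** Visit timing and the unreturned-bottle rule can both lower the value.
- **That taking 14 of the 28 tablets due by a Week 4 stop must be reported as 50%, making 14/14 wrong.** The plan measures adherence up to first failure. If all 14 tablets were taken by Day 14, 100% is correct; it is wrong only if some were taken afterwards.
- **That the cap removes all trace.** It hides the excess in the tables, but Section 4.2.2 also requires a by-subject listing of administration and accountability, where the raw counts stay visible.

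Nor does the SAP say that adherence will be used to separate drug failure from tablets not taken.

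**Conclusion.** The point holds in a narrow form. It is a stated rule that gives a wrong value when followed exactly, not a detail left to the protocol. Material error needs three things together: discontinuation for virologic failure, failure first met between dispensings, and dosing continued from the bottle in hand. In the examples worked, adherence of 50% to 76% up to failure is reported as 86% to 100%, so the subject crosses the 80% line. At dispensing visits the errors are normally small and can go either way, apart from leftover tablets that are kept and taken later.

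The sizes rest on the assumed 28 tablets per dispensing and the assumed later tablets. The number of subjects affected cannot be computed from the SAP and may be zero. A reader might infer that the SVR12 result is at risk. It is not: the estimate by genotype in Section 6.1.2 does not use adherence, and only the three descriptive or exploratory outputs can change. This is a minor correction, worth making because it is cheap.

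**What to change.** Give both terms the same cut-off in Section 4.2.2, and say which quantity results:

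- **(a) Where a tablet count was recorded at the visit of first failure,** end both numerator and denominator at that date. This keeps the quantity the plan intends. Appendix Table 1 has a compliance review at Weeks 1, 2, 4, 8 and 12/ET, but the SAP does not say that a count is recorded at each, so this needs checking against the CRF.
- **(b) Where no such count exists,** calculate the amount prescribed up to the earlier of the last dose date and the day before the first excluded bottle was dispensed. State that the value is then adherence over that dosing period, including any dosing after first failure.

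Under (b), the subject with 10 tablets by Day 14 and one a day for 4 more days has a last dose on Day 18 and scores 14/18 = 77.8%. The subject with 7 and then 5 has a last dose on Day 19 and scores 12/19 = 63.2%. Both fall below 80%.

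The bottle exclusion and the cap can stay. Listing the uncapped value beside the capped one would make any remaining excess easy to see.

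The cost is a sentence or two in the SAP and a small change to the derivation; (b) uses last dose and dispensing dates. A few reported values may be lower. Option (b) also has a real downside, because good dosing after failure can mask poor dosing before it: 9 of 14 before (64%) plus 14 of 14 after gives 23/28 = 82%. It also does not catch leftover tablets from an old bottle taken after a new one is dispensed. Option (a) is therefore preferable wherever the data allow it.
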